8.9. Safety results

Table 48: Reporting Adverse reactions

Relatedness to trial in	Frequency	
Severity:	Not Serious	
	Serious unexpected	
	Serious expected	

Table 49: Adverse reactions

Adverse reaction	Site	Intervention/ Control

Table 50: Serious Adverse reactions

Adverse reaction	Site	Intervention/

Amendments to the SAP

Table 51: Amendments to the SAP

Previous version	Previous date	New version	New date	Brief summary of changes
V2.0	01.06.2017	V2.1	02.11.2017	Comments added following Oxford closure.
V2.1	02.11.2017	V2.2	11.06.2019	Added repeated measures analysis and added analysis to account for timings of clinics and subgroup analysis based on baseline PaSol.

10. APPENDICES

10.1. Stata code for derived variables

```
*BPI severity
qen bpi severity = (worst bl+least bl+average bl+rightnow bl)/4
*BPI interference
gen bpi int =
(interfere gen bl+interfere mood bl+interfere walk bl+interfere norm bl+interfere relation bl+
interfere_sleep_bl+interfere_life_bl)/7
*Oxford knee score
gen oks =
replaced pain bl+replaced wash bl+replaced car bl+replaced walk bl+replaced sat bl+replaced li
mp bl+replaced kneel bl+replaced trouble bl+replaced work bl+replaced giveway bl+replaced shop
_bl+replaced_stairs_bl
* OKS pain subscale
oks pain raw =
replaced pain bl+replaced walk bl+replaced sat bl+replaced limp bl+replaced trouble bl+replace
d_work_bl+replaced_giveway_bl+
oks pain sta = 3.57*oks pain raw
*OKS function subscale
oks func raw =
replaced wash bl+replaced car bl+replaced kneel bl+replaced shop bl+replaced stairs bl
oks func sta = 5*oks func raw
*DN-4
*gen yn feelpain burn bl = .
*replace yn feelpain burn bl = 1 if feelpain burn bl = "yes"
*replace yn feelpain burn bl = 0 if feelpain burn bl = "no"
*gen yn_feelpain_cold_bl =
*replace yn feelpain cold bl = 1 if feelpain cold bl = "yes"
*replace yn feelpain cold bl = 0 if feelpain elect bl = "no"
*gen yn_feelpain_elect_bl = .
*replace yn_feelpain_elect_bl = 1 if feelpain_elect_bl = "yes"
*replace yn feelpain elect bl = 0 if feelpain elect bl = "no"
*gen yn painfeel tingling bl = .
*replace yn painfeel tingling bl = 1 if painfeel tingling bl = "yes"
*replace yn painfeel tingling bl = 0 if painfeel tingling bl = "no"
*gen yn_painfeel_pins_bl = .
*replace yn_painfeel_pins_bl = 1 if painfeel_pins_bl = "yes"
*replace yn painfeel pins bl = 0 if painfeel pins bl = "no"
*gen yn_painfeel_numbness_bl = .
*replace yn_painfeel_numbness_bl = 1 if painfeel_numbness_bl = "yes"
*replace yn painfeel numbness bl = 0 if painfeel numbness bl = "no"
*gen yn painfeel itching bl = .
*replace yn_painfeel_itching_bl = 1 if painfeel_itching_bl = "yes"
*replace yn_painfeel_itching_bl = 0 if painfeel_itching_bl = "no"
*egen dn 4 =
yn_feelpain_burn_bl+yn_feelpain_cold_bl+yn_feelpain_elect_bl+yn_painfeel_tingling_bl+yn_painfe
el pins bl+yn painfeel numbness bl+yn painfeel itching bl
egen dn 4 =
feelpain burn bl+feelpain_cold_bl+feelpain_elect_bl+painfeel_tingling_bl+painfeel_pins_bl+pain
feel numbness bl+painfeel itching bl
```

*PainDETECT

```
gen feelpain_replaced bl score = .
replace feelpain_replaced_bl_score = 0 if feelpain_replaced_bl == 1
replace feelpain replaced bl score = -1 if feelpain replaced bl == 2
replace feelpain replaced bl score = 1 if feelpain replaced bl == 3
replace feelpain_replaced_bl_score = 1 if feelpain_replaced_bl == 4
gen pain detect =
replace pain detect =
(feelpain sting bl+feelpain prick bl+feelpain touch bl+feelpain shock bl+feelpain temp bl+feel
pain_numb_bl+feelpain_press_bl+feelpain_replaced_bl_score+feelpain_radiate_bl)
*HADS
gen hads a =
(mood_wound_bl+mood_fright_bl+mood_worry_bl+mood_relax_bl+mood_butterfly_bl+mood_restless_bl+m
ood panic bl)
gen hads d =
(mood enjoy bl+mood laugh bl+mood cheerful bl+mood slow bl+mood appear bl+mood lookforward bl+
mood book bl)
*Pain Catastrophizing Scale
gen pcs r = (pain away bl+pain mind bl+pain hurts bl+pain stop bl)
gen pcs_m = (pain_worse_bl+pain_events_bl+pain_serious_bl)
gen pcs h =
(pain worry bl+pain can go on bl+pain terrible bl+pain awful bl+pain stand more bl+pain intens
ity bl)
*PaSol
gen pa sol solve =
deal pain search bl+deal pain rid bl+deal pain solut bl+deal pain without bl
gen pa sol meaning =
deal_pain_meaningful_bl+deal_pain_wayout_bl+deal_pain_live_bl+deal_pain_best_bl+deal_pain_way_
hl
gen pa sol accept = deal pain no solution bl+deal pain cntrl bl+deal pain accept bl
gen pa_sol_belief = deal_pain_conf_bl+deal_pain_treat_bl
*ICECAP-A
matrix UTILS=(-0.001,0.101,0.191,0.222\/*
*/-0.024,0.096,0.189,0.228\/*
*/0.006, 0.084, 0.156, 0.188\/*
*/0.021, 0.091, 0.159, 0.181\ /*
*/ -0.003, 0.069, 0.154, 0.181)
gen sta_index=UTILS[1,feel_settled_bl[_n]]
gen att_index=UTILS[2,feel_love_bl[_n]]
gen aut_index=UTILS[3,mood_indep_bl[_n]]
gen ach index=UTILS[4,mood achieve bl[ n]]
gen enj index=UTILS[5,mood pleasure bl[ n]]
gen tariff=sta_index+att_index+aut_index+ach_index+enj_index
*Satisfaction scale
aen
satisfaction scale=(satisfied surgery bl+satis improve bl+satis housework bl+satis leisure bl)
/4
```

*EQ-5D-5L *Used by KG for health econ

11. Bibliography

- Bruce J, T. A., Powell R, Johnston M, Wells M, Heys SD, et al. (2014). Psychological, surgical, and sociodemographic predictors of pain outcomes after breast cancer surgery: A population-based cohort study. *Pain.*, 155(2), 232-243.
- Dworkin RH, T. D., Wyrwich KW, Beaton D, Cleeland CS, Farrar JT, et al. (2008). Interpreting the clinical importance of treatment outcomes in chronic pain clinical trials:
 IMMPACT recommendations. *The journal of pain : official journal of the American Pain Society.*, 9(2), 105-120.

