3.7. Sample size and justification

We estimate that 20% of patients who have had primary total knee replacement will have long-term post-surgical pain. Based on our recent trial in total knee replacement (Wylde V, 2015), we estimate conservatively that we will achieve a recruitment rate of 40% (an 8% conversion rate for number randomised out of those screened). Surgical audit data show that the four trial centres conduct over 1,900 primary total knee replacement procedures annually. Over 30 months, this equates to 4,750 procedures, and we estimate that 950 of these patients will have long-term post-surgical pain. With a recruitment rate of 40% we can recruit 380 patients over this period. In our recent trial we achieved 83% follow-up (Wylde et al, 2015); therefore, allowing for a generous 25% loss to follow-up in the STAR trial, a total of 380 participants randomised would yield 285 for analysis. For a 2:1 intervention:control randomisation ratio we would have a power of 80% to 90% to detect standardised differences of between 0.35 to 0.40 standard deviations (SDs) using a 2-sided 5% significance level. From previous studies (Dworkin RH, 2008), (Bruce J, 2014), the SDs for each of the BPI Interference and Pain Severity scales for patients with long-term postsurgical pain has been observed to be approximately 2, in which case the target effect size translates to a difference between intervention and control groups of between 0.7 and 0.8 scale points for both scales. Such a difference would be worthwhile detecting clinically, since the current consensus statement indicates that differences of approximately one scale point can be deemed the minimally important difference for both of these scales (Bruce J, 2014),(Kroenke K, 2009).

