4.2. Derived variables

Co-primary outcome measures

The Brief Pain Inventory is a questionnaire which consists of 14 questions. Eleven of which are included in Section A of the follow-up questionnaire for STAR. The two scores which will be used as our co-primary are described below.

- Pain Severity Score: The Pain Severity Score is calculated by taking the mean of the rating scores of the first four questions in Section A of the questionnaire (Q1+Q2+Q3+Q4)/4.
- Pain Interference Score: The Pain Interference Score is calculated by taking the mean of the last seven questions in Section A of the questionnaire (Q7+Q8+Q9+Q10+Q11+Q12+Q13)/7.

Secondary outcome measures

• Oxford Knee Score (OKS)

The OKS is calculated using the items in section B of the questionnaire. To calculate the OKS, we sum the responses to the 12 items (individual items scored 0-4, worst to best). The total score has a range of 0-48 (worst to best). The Oxford Knee Score can be split into two subscales: the pain and function subscales.

- OKS Pain subscale: the raw subscale is equal to the sum of the responses to the following questions: 1, 4, 5, 6, 8, 9 and 10. This is then standardised to range from 0 to 100 by multiplying by 3.57.
- OKS Function subscale: the raw subscale is equal to the sum of the responses to the following questions: 2, 3, 7, 11 and 12. This is then standardised to range from 0 to 100 by multiplying by 5.
- PainDETECT

The PainDETECT score is calculated using items in Section C of the questionnaire. The first seven questions are scored zero to five (Never – Very Strong). The eighth question is a picture representation of the pain and these are scored between negative one and positive one. Lastly the ninth question is scored 2 if "Yes" is selected and zero if "No" is selected. The sum of each score provides the PainDETECT score. This ranges from -1 to 38 and scores fall into three categories: (-1 to 12) nociceptive, (13-18) unclear and (19-38) neuropathic pain.

• DN-4

The DN-4 score is a score out of 7 corresponding to the number of 'yes' answers the patient gave in Section D.

• EQ-5D-5L

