4.3 Procedures for missing data

In all tables missing data will be indicated by footnotes. If the amount of missing data differs substantially between treatment groups potential reasons will be explored. Sensitivity

analyses will be conducted (including the use of multiple imputation by chained equations (mice) methods) to examine the influence of missing data on the key trial findings. When using mice, 25 datasets will be generated and 10 switching procedures undertaken. The imputation model will include all variables predictive of missingness, together with all of the variables included in the main substantive model. Comparisons of results from ITT analyses of complete cases with ITT analyses where missing data were imputed will be presented in **Table 17 - Table 29**.

The model used for imputation will include a baseline measure of the outcome, any other observations of the outcome at different follow-up times, randomisation group, age/gender, centre and any other restriction variables for the randomisation (i.e. stratification/minimisation), we will consider also including any other variables that are either strongly associated with missingness or likely to have some prognostic value. This list will be finalised before conducting the mice analyses.

In the event of missing data, we will follow guidelines where applicable and use mice to impute scores if the missingness exceeds the guidelines.

BPI (severity and interference): The first four items of section A must be complete to calculate the score for the severity scale. Four of the last seven items of section A of the questionnaire must be complete to calculate the interference scale by averaging complete items.

OKS: If 1 or 2 questions are missing, then the mean value can be used to fill the gaps.

PainDETECT: If any of the first seven items of section C are missing impute with the mean of the complete items in the first seven items. If question 8 of section C is missing do not add or subtract anything from the score (ie. Treat the value of that item as zero). If question 9 is missing, assume the response is no, thus, treat the value of the item as zero.

DN-4: No score can be calculated if more than 4 items are missing. The score is a proportion of "Yes" responses.

Short form-12: The short form-12 requires 50% of items to be completed.

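### The appendix scoring code does not apply the missing-item rules of section 4.3, and section 4.3 describes DN-4 on a different scale from the rest of the SAP

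*SAP*

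**What the plan says.** **BPI Interference.** SAP section 4.2 defines the score as the sum of seven items divided by 7. Section 4.3 adds a rule for blanks: "Four of the last seven items of section A of the questionnaire must be complete to calculate the interference scale by averaging complete items". The code in appendix 10.1 joins seven baseline variables with plus signs and ends "interfere_sleep_bl+interfere_life_bl)/7". It does not count completed items, take a row mean or fill blanks beforehand.

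**Other scales.** Section 4.3 also allows some blanks for OKS, PainDETECT, HADS, the Pain Catastrophizing Scale (PCS), PaSol, ICECAP-A and satisfaction. The appendix scores each of these by plain addition; for ICECAP-A it adds looked-up tariff values.

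**DN-4.** Section 4.2 says "The DN-4 score is a score out of 7 corresponding to the number of" yes answers, Table 13 gives the range as 0-7, and the code adds seven items. Section 4.3 permits a score with up to four items missing and then says "The score is a proportion of" yes responses. Nothing rescales that proportion to 0-7.

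**Context.** Section 1 says the plan should be detailed enough for someone else to run the analysis. Section 4.1 makes the primary analysis complete case. Sections 7.3 and 7.4.2 adjust for baseline BPI.

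**The concern.** In Stata, `+` returns missing if any operand is missing. A statistician who took over and ran the appendix would get no baseline Interference score for a patient whom section 4.3 says can be scored. Because the primary analysis is complete case and adjusts for baseline BPI, a missing baseline score can remove that patient from the model. Multiple imputation is planned only as a sensitivity analysis, so it would not restore the patient to the primary result. Tables 5 to 8 count questionnaires complete enough to be scored, so they too depend on which version is run.

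The DN-4 problem is different. If section 4.3 is read literally as a rule for incomplete records, partial responders get a value between 0 and 1 and complete responders a value between 0 and 7, in the same column.

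**Working it through.** **1. The plan's own figure.** Section 3.7 states that "a total of 380 participants randomised would yield 285 for analysis", and 380 × 0.75 = 285. At 2:1 this is 190 and 95. With a two-sided 5% level the standard error of the standardised difference is √(1/190 + 1/95) = 0.1257.
- At 0.35 SD: 0.35/0.1257 − 1.96 = 0.825, power 79.5%.
- At 0.40 SD: 0.40/0.1257 − 1.96 = 1.223, power 88.9%.

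The stated 80% to 90% is reproduced, so the sample size is not in question.

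**2. One worked record.** Take Interference items 5, 6, 7, 4, 3, 8 and one blank.
- Section 4.3: six items are complete, so the score is 33/6 = 5.5.
- Appendix code: the sum contains a missing term, so there is no score.
- Filling the blank with 5.5 first and then running the code: 38.5/7 = 5.5, which matches the rule.

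**3. Scale by scale.** The code needs every item for every scale below.

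| Scale | What section 4.3 allows | Code agrees? |
|---|---|---|
| BPI Severity | no blanks of 4 | yes |
| BPI Interference | up to 3 blanks of 7 | no |
| OKS | 1 or 2 blanks, mean-filled | no |
| PainDETECT | blanks in items 1-7 mean-filled; blank item 8 or 9 counts as zero | no |
| HADS | 1 blank per subscale | no |
| PCS | 1 blank per subscale | no |
| PaSol, 4 and 5 items | 75% complete: 3 of 4; 3.75, so 4 of 5 | no |
| PaSol, 3 and 2 items | 75% is 2.25 and 1.5, so all items | yes |
| ICECAP-A | 1 blank, mean-filled | no |
| Satisfaction | 1 blank, mean-filled | no |

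**4. DN-4.** Up to four missing means at least 7 − 4 = 3 answered.
- 3 yes of 7 answered: count 3, proportion 3/7 = 0.43, prorated 7 × 3/7 = 3.0.
- 3 yes of 6 answered: count 3, proportion 3/6 = 0.50, prorated 7 × 3/6 = 3.5; the printed sum gives missing.

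**5. Illustrative loss for Interference.** Let q be the chance that an item is left blank, independently across seven items. Both q and independence are assumptions; the SAP gives no rate.
- Lost under the code: 1 − (1 − q)^7 = 6.8%, 13.2% and 19.2% at q = 1%, 2% and 3%.
- Lost under the rule: P(at least 4 of 7 blank), at most 0.003% at these rates.

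**The case against.** The best defence is that the SAP does say what happens to blanks. Section 4.3 commits to following the scale guidelines and then imputing, so the four-of-seven rule governs. The appendix, which shares its subject with section 4.2, can be read as setting out only the complete-item formulas. Step 2 shows that filling blanks first makes the printed Interference code agree with the rule. This stands: the Interference definition is not undecided, and the fault is a missing step in the code. But the SAP does not print or mention that step for Interference, and it is meant to be usable by a replacement statistician.

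A reader might infer that co-primary outcomes will be lost, for example 19, 38 or 55 of 285 (285 × 6.8%, 13.2% and 19.2%). The document does not support that. Every item variable in the code carries the baseline suffix, 285 is the number expected at final analysis, and nothing says the formula is reused at 6 or 12 months. Baseline loss should also be limited: section 3.6 minimises on baseline Interference, so a usable score is needed at randomisation, and section 6.2 has assessors telephone patients about missing items. If blanks cluster within patients, fewer questionnaires are affected at the same item rate.

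On DN-4, the word proportion may be intended to mean prorating. With complete data, dividing by 7 changes the units of the estimate and not the test. A reader might infer a sevenfold error in the DN-4 result, but that goes too far. The real risk is mixed scales when some records are incomplete.

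**Conclusion.** The point holds as a mismatch between the printed code and the stated rules. As printed, one blank item gives a missing baseline Interference score that section 4.3 would calculate, and the scales marked no in the table share the fault. DN-4 has two descriptions that a literal reader would mix.

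The mismatch itself is certain from the text, given how Stata adds missing values. Its numerical effect is unknown. The 6.8% to 19.2% range rests wholly on assumed, independent item blank rates of 1% to 3% and is an illustration, not a forecast. Loss of 6- or 12-month outcomes would follow only if the same formula were reused. Because the repair is cheap and protects a co-primary score and a baseline covariate in a complete-case analysis, it should be made before the analysis is run.

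**What to change.** - Code Interference with `egen` `rowmean` over the seven items, set to missing when `rownonmiss` is below 4.
- For the other mismatched scales, put the section 4.3 fill or prorating step ahead of the existing sum. Leave BPI Severity and the two- and three-item PaSol subscales as they are.
- State that the same derivations apply at baseline, 6 and 12 months.
- Define DN-4 as 7 × (yes answers / items answered) when at least three items are answered, and missing otherwise. This keeps the section 4.3 threshold and the 0-7 range of Table 13. Replace the DN-4 sentence in section 4.3 and the DN-4 code line accordingly.

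The cost is a few lines of code and one or two sentences, logged in Table 51. No design feature, model or sample-size figure changes.
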